(breaking point) or the session ends. The maximum response ratio completed that resulted in reinforcement provides a quantifiable measure of motivation to drink. A second reinforcer (\$1 per unit) is included to permit examination of relative rates and distribution of responses between the two reinforcers. Using the NIAAA definition of a standard drink unit (SDU, 14 g alcohol), each alcohol reinforcer equals 0.5 SDU (7 g alcohol). Alcohol content was standardized to 0.5 SDU to ensure equivalency across subjects for amount of alcohol. A maximum of 10 reinforcers (money and alcohol) is available. The response ratio requirement begins at 400 and increases by a factor of 1.2 (400, 480, 576, 692, 830, 995, 1194, 1433, 1720, 2064). We will administer a priming drink (0.5 standard drink of alcohol (liquor type is based on subject preference) immediately before the AMR. This drink volume is sufficient to increase craving or desire to drink in heavy drinkers without producing a significant increase in blood alcohol levels or interfering with responding under the PR procedure. Participants will complete self-report measures of alcohol craving and alcohol effects following drink completion, and then begin the AMR session.

The AMR session will terminate after 60 min, or after no response occurs for 10 min, whichever occurs first. Alcohol is not available for consumption until 60 min elapses. After 60 min, participants receive money vouchers and self-administer earned drinks of their preferred liquor (vodka or whiskey). Subjects will be allowed up to 90 minutes to finish drinking; Staff will provide drinks paced to ensure that subjects cannot exceed 0.5 SDU every 5 min or all earned drinks (5 SDU maximum) in a 50-minute period. A preferred mixer and snacks is provided. Using this procedure, we have established a baseline in which high levels of responding were maintained. Subjects distribute responses to earn about half of available alcohol drinks on average. We targeted this distribution to 1) avoid a floor effect in which response cost is too high, and subjects stop responding, 2) prevent a ceiling effect in which all 10 drinks are obtained, and 3) allow detection of either increases or decreases in drinks during OT treatment.

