Cumulative Alcohol Dosing (CAD). On day 6, subjects will complete a CAD procedure in which 1 placebo and 3 active alcohol drinks are administered at timed intervals to increase BAL progressively (0.03-0.1%). Subject doses will be determined using a Computerized Blood Alcohol Calculator^[99] which adjusts for age, height and gender differences in body water and time spent drinking, to target similar BAL in males and females. IDS will prepare each 120 mL drink by mixing the appropriate mL of 95% ethanol in a sweet beverage using a w/v metric. The placebo drink is blinded by floating 1 mL ethanol on top of the drink and by placing an ethanol-soaked wristband around the glass to deliver a strong alcohol odor. Active alcohol drinks are prepared the same. Staff monitor subjects and ensure consumption of each drink is paced over 10 min. Subjects will complete a computerized subjective report battery at baseline (-30 minutes) and every 30-min. The 10-min computerized battery is shown in **Table 3**. The placebo drink will be administered at time 0, followed by active alcohol drinks at 30 min intervals. Breath alcohol levels (BAL) will be determined at baseline and 15 min after each drink. Heart rate, skin conductance, skin temperature and blood pressure are recorded via a noninvasive monitor. Subjects return to the CRU for monitoring, and complete the battery and an Alcohol Hangover Scale^[100] every hour for 4 hours post session and once the next morning. We have safely administered alcohol in social and heavy drinkers^[83, 100-102], and demonstrated reliable alcohol dose-related increases in heart rate and subjective effects; these effects are sensitive to AUD medications (naltrexone, acamprosate)^[103-106]. The CAD was chosen to reduce subject research burden and dropout rates.

Table 3: Computerized battery of subjective report measures for CAD session

Drug Effect Visual Analog Scale (VAS) includes the following questions: "Do you feel ANY effect of the drink(s)?," "Do you feel GOOD effects from the drink(s)?," "Do you feel BAD effects of the drink(s)?," "Do you LIKE the effects of the drink(s)?," "Do you DISLIKE the effects of the drink(s)?," "Is this the WORST you have ever felt?", and "Is this the BEST you have ever felt?". Subjects respond by positioning an arrow on a 100-point line anchored by "not at all" and "extremely."

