Ethyl Alcohol/Alcohol: Alcoholic beverages are legally sold to adults. The dose of alcohol used in the CAD was selected to bring blood ethanol levels to approximately 0.1% was determined based on our previous studies and a comprehensive literature on administering alcohol to research subjects. This BAC corresponds to about 1 g/kg alcohol. The drink is prepared by IDS using 190 Proof ethanol (95%v/v, 0.775 g/ml Spectrum Chemical); the total alcohol dose is divided over three drinks, prepared by mixing the appropriate amount of pure ethanol with a sweet beverage. Using standardized drinking units, 1 (e.g. (One standard drink is equivalent to 12 ounces of beer, 5 ounces of wine, or 1.5 ounces of 80-proof spirits.), this amount is about 4-5 drinks for men and about 3-4 drinks for women when consumed in over 2-hour drinking episode. This amount is within the limits of the typical drinking episode of participants, and are not expected to produce significant adverse events.

After the AMR, subjects may consume up to up to 5 standard drinks (70g ethyl alcohol) of an alcoholic beverage of their choice (e.g., beer, wine or liquor) during the alcohol self-administration session, and drinking is paced. These amounts are within the limits of the typical drinking episode of participants and also are sufficiently large to promote alcohol-motivated responding.

Use of intranasal OT and alcohol will be under FDA-approval via IND 110,562 (holder [name], Co-I, *amendment submitted to FDA 8/4/14*). Amendment application is uploaded to eIRB protocol.

Nicotine Patch: Active nicotine patch (21 mg) is the standard of care for management of nicotine withdrawal.

b. Justification and safety information if FDA approved drugs will be administered for non-FDA approved indications or if doses or routes of administration or participant populations are changed.

n/a

c. Justification and safety information if non-FDA approved drugs without an IND will be administered.

n/a/

7. Study Statistics

a. Primary Outcome variables:

- Peak scores for CIWA-Ar and Craving Scales for abstinence days 1-3.
- Total and subscale scores on POMs Short at assessment and during the CRU stay
- UFC for abstinence days 1-3
- Peak salivary CORT in the TSST
- Number of drinks earned in the AMR
- Peak drug effect VAS scores and peak increase in heart beats per minute (bpm) in the CAD

b. Secondary Outcome variables:

- Stimulation and sedation subscales of the BAES in the CAD

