- vii. *Trier Social Stress Test (TSST):* Subjects will participate in the Trier Social Stress Test as part of the experimental protocol. This test includes public speaking and mental arithmetic components, which have been shown to elevate a variety of physiological measures, including neuroendocrine and autonomic variables. There is a small risk that clinically significant symptoms of anxiety or grossly elevated autonomic reactivity may occur. We have completed the Trier Stress Test (TSST) in over 400 subjects without inducing serious mental or physical distress. This includes completing the TSST in 27 alcohol dependent subjects. Participants are monitored throughout the procedure.
- viii. *Alcohol procedures (AMR and CAD):* Alcohol may produce mood and behavioral effects that are dysphoric and that can result in impairment in performance and judgment and, in cases of overdose, ethanol can produce medically serious toxic effects. In the AMR and alcohol self-administration session, the maximum dose of alcohol that subjects can self-administer is five standard drinks over 50 minutes; this dose will produce a blood ethanol level of approximately 120mg/dL. In the CAD session, the maximal proposed dose is one that produces a blood ethanol level of approximately 100mg/dL. Subjects invited for study participation are those who regularly drink doses of ethanol greater than the doses selected in this study, reducing the likelihood of adverse events. These are medically safe but behaviorally intoxicating levels, associated with impairment of psychomotor and cognitive performance and with emotional and behavioral effects that may range from sedation and drowsiness to agitation, irritability, depression, and emotional lability. These effects dissipate as blood ethanol levels decline.

ix. *IV placement and fluid delivery.* IV placement can cause some pain. There is a slight risk of bleeding, bruising, or irritation whenever blood is drawn or IV lines are started. In addition, IV fluid can occasionally escape under the skin, causing pain and swelling for a few days. When an intravenous product is given, there is always a chance that the needle placed in the vein may infiltrate causing temporary swelling, bruising, bleeding and/or discomfort. The risk of temporary clotting of the vein is about 1%. In rare cases, fainting or infection may occur.

b. Steps to Minimize Risks.

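### Is the single blood ethanol figure of about 120 mg/dL for the AMR maximum wrong for women?

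*Protocol*

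**What the plan says.** The protocol, Section 8.a.viii (Alcohol procedures), gives one expected level for the largest amount a subject can drink after the AMR task: "five standard drinks over 50 minutes; this dose will produce a blood ethanol level of approximately 120mg/dL". It makes no distinction by sex or body weight and calls the AMR and CAD levels medically safe.

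Section 4.a (Alcohol Motivated Responding) fixes the amount of alcohol for everyone: "Alcohol content was standardized to 0.5 SDU to ensure equivalency across subjects for amount of alcohol". Pacing ensures that subjects cannot exceed "all earned drinks (5 SDU maximum) in a 50-minute period", although they may take up to 90 minutes. The cap equals 70 g (Section 6.a). The same part of Section 4.a reports of earlier use of the task: "Subjects distribute responses to earn about half of available alcohol drinks on average".

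The cumulative alcohol dosing (CAD) session is handled differently. Its dose is individual and comes from a calculator that "adjusts for age, height and gender differences in body water and time spent drinking, to target similar BAL in males and females".

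Section 6.a describes the CAD target of about 0.1% (100 mg/dL) in two ways. By weight: "This BAC corresponds to about 1 g/kg alcohol". By drinks: "this amount is about 4-5 drinks for men and about 3-4 drinks for women when consumed in over 2-hour drinking episode".

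**The concern.** The CAD dose is adjusted so that men and women reach similar levels. The AMR amount is not adjusted, yet its expected level is stated as if it were the same for both sexes. Section 6.a itself says that women need fewer drinks than men to reach 100 mg/dL, so five equal drinks should take women higher. Half of the planned accrual is women (12 of 24, Section 4.a, Design Overview), and the safety wording in Section 8.a.viii refers to the quoted levels. If 120 mg/dL described men only, the risk section would understate the expected exposure for half the sample at the cap.

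**Working it through.** **Inputs.** AMR maximum: 5 standard drinks, 70 g, over 50 minutes, about 120 mg/dL (Sections 6.a and 8.a.viii). One standard drink: 14 g (Section 4.a). About 100 mg/dL: 4-5 drinks in men and 3-4 in women over 2 hours, or about 1 g/kg (Section 6.a). The protocol gives no formula for 120 mg/dL, no elimination rate and no body weights, so 120 cannot be reproduced directly. It can only be set against the two descriptions.

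**What 120 implies.** If five drinks give 120 mg/dL, then 100 mg/dL takes 5 / 1.2 = 4.17 drinks. That is inside the men's range and 0.17 drink above the upper edge of the women's.

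**By drink count.** Level = 100 × 5 / k, where k is the number of drinks that gives 100 mg/dL.

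| Group | k | Level at five drinks (mg/dL) | Ratio to 120 |
|---|---|---|---|
| Men | 5 | 100 | 0.83 |
| Men | 4.5 | 111 | 0.93 |
| Men | 4 | 125 | 1.04 |
| Women | 4 | 125 | 1.04 |
| Women | 3.5 | 143 | 1.19 |
| Women | 3 | 167 | 1.39 |

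The stated figure fits the men's range. It also fits women at 4 drinks, within the meaning of approximately. It is low for women at 3 to 3.5 drinks.

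**By weight.** Level = 100 × 70 / weight in kg. This equals 120 at 70 / 1.2 = 58.3 kg. For assumed weights it gives 140 at 50 kg, 117 at 60 kg, 100 at 70 kg and 88 at 80 kg, for either sex. Above about 58 kg the stated 120 is too high on this description, not too low.

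**What depends on the figure.** The cap (5 SDU) and the pacing (at most 0.5 SDU every 5 minutes) are set in drinks. The AMR primary outcome is the number of drinks earned (Section 7.a). Under Section 4.a earned alcohol is not available until the 60-minute task period is over, so that outcome is settled before any earned drink is consumed. The CAD doses come from their own calculator. In Section 8.b a physician is called when a subject shows an adverse effect, not at a blood level. None of these uses 120 mg/dL.

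**How often the cap should matter.** Half of the 10 available reinforcers is 5 × 0.5 = 2.5 standard drinks. By the same proportion that gives 100 × 2.5 / 5 = 50 to 100 × 2.5 / 4 = 62.5 mg/dL in men, and 62.5 to 100 × 2.5 / 3 = 83 mg/dL in women. This is an average, so some subjects may still reach the cap.

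**The case for a change.** The strongest argument for acting is that simple proportion may understate the gap. The counts in Section 6.a are spread over 2 hours and the AMR maximum over 50 minutes. With an elimination rate b per hour, the level becomes 5 × (100 + 2b) / k − b × 50/60. The protocol gives no b. Over an assumed 10 to 25 mg/dL per hour, women come to 142-192 at the low rate and 167-229 at the high rate, and no count for women then gives 120. The half-drink prime is also left out. With it, 5.5 drinks by simple proportion give women 138-183 and men 110-138. A risk section that states a maximum should not be low for either sex.

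Part of this stands. On the drink counts, 120 mg/dL is more likely low than high for women, and one sex-neutral figure is a loose way to describe a fixed dose. But the size of the gap rests on rates that the document does not give. The same allowance moves men to 112-142 at the low rate and 129-167 at the high rate, so the neat contrast between a figure that fits men and one that fails women depends on the method. Fifty minutes is also the fastest permitted pace, since subjects may take 90 minutes and have snacks.

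A second argument is that the two descriptions in Section 6.a agree only at certain weights: 4-5 drinks × 14 g = 56-70 g, hence 56-70 kg for men at 1 g/kg, and 3-4 drinks = 42-56 g, hence 42-56 kg for women. Without body weights in the protocol this cannot be called an error. It also has no effect on CAD dosing, which is calculated for each subject.

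**Conclusion.** No change to the plan follows. By direct proportion from the drink counts, five drinks give 100-125 mg/dL in men and 125-167 mg/dL in women, so the stated 120 is low for women at 3 to 3.5 drinks by the protocol's own counts. The weight description points the other way above about 58 kg. The document therefore shows two rough descriptions that do not meet exactly, not that the approximate figure is wrong, and it does not show what the true level would be.

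The figure occurs in a description of risk. No endpoint, analysis, drink cap, pacing rule or monitoring step takes it as an input, so restating it by sex would make the text clearer without altering what the trial does or can conclude. This rests on direct proportion, on 14 g per drink and on assumed weights of 50-80 kg. It makes no judgement on whether any of these levels is clinically acceptable.

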Our laboratory has substantial experience administering ethanol to human subjects under a variety of experimental and dosing conditions. All ethanol doses are administered under doctor's orders and prepared by the Johns Hopkins Investigational Drug Service using the participant's preferred alcoholic beverage (e.g., beer, wine or liquor for AMR and self-administration) or pharmacy-grade ethanol (for CAD). Participants are monitored carefully throughout the laboratory sessions; should a subject evidence a medical or behavioral adverse effect, a physician will be called immediately and the subject will receive appropriate evaluation and treatment. Thus, the careful choice of doses, the medical observation and monitoring, and the use of human volunteers who regularly drink doses of ethanol comparable to and greater than the ones selected for this study render the likelihood of serious adverse ethanol-induced effects unlikely.

- ix. *Confidentiality:* Our staff is well trained in the matters of confidentiality. Subject numbers will be used to code all data forms for computer entry and storage. Study findings are reported using group data only. No information about subjects will be provided to anyone outside of the study including family members, third persons or organizations. Experimental sessions will take place in the Johns Hopkins 550 Building and the Johns Hopkins Clinical Research Unit. We will obtain a Certificate of Confidentiality for this study from the funding agency.
- x. *IV placement and fluid delivery.* To minimize risks, only experienced medical personnel using sterile equipment will be performing IV placements and fluid delivery, and procedures are completed on the CRU.

c. Plan for reporting unanticipated problems or study deviations

An adverse event (AE), is defined as any untoward medical occurrence in a subject, not necessarily having a causal relationship with the study. A serious adverse event (SAE) is any untoward medical occurrence that a) results in death, b) is life-threatening, c) requires inpatient hospitalization or prolongation of existing hospitalization, d) results in persistent or significant disability/incapacity, or e) is a congenital anomaly/birth defect.

AE's may be graded as: Mild (no limitation of usual activities), Moderate (some limitation) or Severe (inability to carry out usual activities). The relationship of the AE to the study procedures is classified as: Not related, Unlikely, Possible, Probable, or Definite.

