[name] has responsibility for communication with the IRB and will be responsible for distinguishing between an AE and SAE. SAEs that are deemed to be severe and have a high probable or definite relationship to study procedures will be reported to the Johns Hopkins Medical Institute IRB and NIAAA project officers within 48 hours.

Annual reports will be submitted to the NIAAA project officer and the IRB summarizing protocol deviations, as well as AEs and how they were addressed by the study team. [name] (holder of the IND) will be responsible for all reports to the FDA per their guidelines and regulations.

d. Legal risks such as the risks that would be associated with breach of confidentiality.

Subject numbers will be used to code all data forms for computer entry and storage. Study findings are reported using group data only. No information about subjects will be provided to family members, third persons or organizations. Experimental sessions will take place in the Johns Hopkins 550 Building, the Johns Hopkins CRU and the JH Bayview CRU. Our study personnel are trained in the protection of human subject confidentiality and are HIPAA trained and certified.

e. Financial risks to the participants.

All costs for the CRU stay and study related procedures will be covered by NIH grants.

9. Benefits

a. Description of the probable benefits for the participant and for society.

This study is conducted for the advancement of science. It is clinically and scientifically important to determine the effects of OT on alcohol withdrawal symptoms, stress response, alcohol motivation, consumption and sensitivity in heavy drinkers during acute alcohol abstinence. These studies will provide new information that is relevant for the development of OT as a potential pharmacotherapy for AUD.

At the end of study participation, subjects receive a brief psychosocial intervention for their heavy drinking. Brief psychosocial intervention has been shown to be efficacious in reducing alcohol consumption and alcohol-related problems.

10. Payment and Remuneration

a. Detail compensation for participants including possible total compensation, proposed bonus, and any proposed reductions or penalties for not completing the protocol.

Since participants receive payment depending on which parts of the protocol they participate we have divided payments into payment for procedures for study eligibility and procedures for study completion.

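### The 48-hour SAE report to the IRB and NIAAA excludes serious events rated Possible or graded Moderate, and uses a relatedness term that the protocol does not define

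*Protocol*

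**What the plan says.** Section 8.c of the protocol sets out three separate attributes of an adverse event.

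- **Seriousness** is defined by outcome: death, threat to life, hospitalization, lasting disability or birth defect. An event that "requires inpatient hospitalization or prolongation of existing hospitalization" is serious on that ground alone.
- **Severity** is graded as "Mild (no limitation of usual activities), Moderate (some limitation) or Severe (inability to carry out usual activities").
- **Relatedness** is "classified as: Not related, Unlikely, Possible, Probable, or Definite".

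The expedited rule follows: "SAEs that are deemed to be severe and have a high probable or definite relationship to study procedures will be reported". The recipients and time limit are given in the same sentence, in which these events are "reported to the Johns Hopkins Medical Institute IRB and NIAAA project officers within 48 hours".

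Two other routes are stated. One is yearly: "Annual reports will be submitted to the NIAAA project officer and the IRB summarizing protocol deviations", and it also covers AEs and how they were handled. The other goes to the FDA: the IND holder "will be responsible for all reports to the FDA per their guidelines and regulations".

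**The concern.** Seriousness is normally what makes a report urgent. Here it is necessary but not sufficient: the event must also be graded severe and attributed to study procedures with high confidence. One of the two attribution terms used for that test is not on the scale that staff are told to use.

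This matters more than usual because attribution will often be uncertain. Subjects have alcohol use disorder, undergo supervised abstinence, receive an investigational drug three times daily, and are then given alcohol in two sessions. A serious event has several candidate causes, so Possible is a plausible rating. Hypothesis 4c makes adverse interactions between oxytocin and alcohol a study question. If such a signal appeared as an SAE of uncertain cause, the two oversight bodies named in 8.c might not learn of it while enrolment continued.

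**Working it through.** No power, alpha or sample-size figure is involved, and the plan states no figure to reproduce. The check sets the rule against the protocol's own definitions.

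**Step 1: the trigger.** As written, a 48-hour report requires all of: (a) SAE by outcome, (b) graded Severe, (c) relationship *high probable* or Definite.

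**Step 2: the terms.** Severe and Definite are both defined levels in 8.c. *High probable* is not. It may mean Probable, or only the upper part of Probable, and the text does not settle which.

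**Step 3: example events run through the rule.**

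| Event | Severity | Relatedness | 48-hour report? |
|---|---|---|---|
| Life-threatening event | Severe | Definite | Yes |
| Hospitalization | Severe | Probable | Unclear (*high probable*) |
| Death | Severe | Possible | No |
| Hospitalization | Moderate | Definite | No |
| Hospitalization | Moderate | Possible | No |

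A death would presumably be graded Severe, so for deaths the relatedness filter decides. For hospitalizations either filter can exclude the event.

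**Step 4: other routes to the IRB or NIAAA.** The annual report is the only one stated. It is described as "summarizing protocol deviations, as well as AEs and how they were addressed by the study team", and since SAEs are a subset of AEs it would include them, but up to 12 months later. The safety steps in 8.b (calling a physician, nurse practitioner or investigator) are internal to the study. The early stopping rules in 7.d govern individual subjects and notify neither body.

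**Step 5: is such an event foreseeable?** Yes. Section 8.a lists seizures among the risks of detoxification. The alcohol abstinence text in 4.a provides for moving a removed subject to medical care. That move is an SAE if it amounts to hospitalization or prolongs it.

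**Step 6: size.** The protocol gives no SAE rate and no accrual rate. After a first event, the other subjects who could be exposed before an annual report number at most 24 − 1 = 23; the likely number cannot be derived. Section 8.b says that over 98% of earlier alcohol-dependent subjects came through withdrawal without medication that required termination. If that carried over, fewer than 0.02 × 24 = 0.48 subjects would be expected to need it. This is not an SAE rate and covers withdrawal only, but it suggests a low count.

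**The case against.** The strongest reply is that this is a deliberate threshold. Seriousness, severity and relatedness are defined separately, and a rule that requires all three is coherent. Nothing in the protocol says that every SAE must be expedited, so asking for SAEs rated Not related goes beyond reconciling the text. That stands, and it is why the minimum fix below stops at Possible.

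Second, most SAEs would probably be graded Severe, since Severe means being unable to carry out usual activities and SAEs are grave by definition. That also stands. A tally of severity-by-relatedness combinations would therefore say nothing about how many real events are missed. The gap that matters is Severe with Possible, and Moderate with Possible or higher. A withdrawal complication might also be rated Probable or Definite, since supervised withdrawal is itself listed as a procedure.

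Third, IRB policy outside the document may require more. It may, but 8.c does not refer to any such policy, and staff will work from the written rule.

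Fourth, subject care does not depend on this report, because 8.b calls for immediate physician or investigator involvement. That is correct. What is at stake is oversight of the remaining subjects.

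**Conclusion.** The point holds for reporting to the IRB and NIAAA. The expedited rule contains one undefined term and leaves SAEs rated Possible or graded Moderate with no stated route to those bodies except the annual summary. It is a stated rule with a safety consequence, and it should be corrected. The number of events affected is likely small but cannot be estimated. The conclusion assumes that the rule is followed as written and that no unstated policy overrides it.

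Four stronger readings are tempting, and the protocol does not support them.

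- *The FDA would also wait for the annual report.* It would not follow: FDA reports are assigned to the IND holder under FDA rules.
- *The rule contradicts the SAE definition.* It is narrower than the definition, which is not a contradiction. The only mismatch is *high probable*.
- *Relatedness to the study drug is never rated.* Section 8.a lists oxytocin administration among the study's procedures, so the word can be read to include the drug.
- *Blinded staff rate relatedness, which weakens the rating.* The protocol does not say who rates relatedness, and blinded rating in a double-blind trial is not a defect.

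**What to change.** Reword the one sentence in 8.c so that SAEs as defined there go to the IRB and NIAAA within the existing 48 hours. Remove the requirement that the event be graded severe. Replace *high probable* with the defined relatedness levels, and include at least Possible, Probable and Definite. Reporting every SAE whatever its relatedness is the simplest version with 24 subjects, because no attribution is then needed before sending the report. The annual summary and the separate FDA route can stay as they are.

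The cost is a protocol amendment of one sentence and a few extra expedited reports. No dose, eligibility rule, clinical procedure or analysis changes.
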